c. Treatment assignment and randomization. All study participants will receive the same treatment procedures. No assignment or randomization is required.

V. STUDY PROCEDURES

a. Study visits and parameters to be measured: Participants will have the option to participate at the MGH IHP, at their home, or via Enterprise Zoom.

Once participants are consented, the typical study sequences include (*also in Figure 1*): Each step is described in additional detail in the section that follows.

- 1) Pre-treatment: Completion of pre-treatment cognitive-linguistic assessments, naming probes, and spontaneous speech probes (sessions approximately 2 hours in length over an average of 3-5 days to mitigate any effect of fatigue on assessment performance).
- 2) During Treatment: Participation in the treatment for a period of eight weeks. All participants will receive the same treatment. Participants will receive in-person therapy at the MGH Institute of Health Professions, home visits, or virtual sessions (via Zoom). Participants will attend three 70-minute treatment sessions per week for eight consecutive weeks. Treatment sessions will be conducted by a certified SLP. Starting on Week 2, the first treatment session of each week will begin with a 30-minute assessment, consisting of a naming probe, a connected speech probe, and a strategy knowledge probe, in which the participant will be asked to provide the six strategy components. Treatment will stop at the end of the eight weeks, or after three consecutive naming probe performances over 90% accuracy, whichever occurs first.
- Post-treatment re-administration of assessments: Participants will complete the same cognitive-linguistic assessments, naming probes and spontaneous speech probes as they did pre-treatment within 20-30 days following the last treatment session. Sessions will last approximately 2 hours in length over an average of 3-5 days.
- 4) Post-treatment tests of retention: Participants will attend two additional post-treatment sessions one month and two months after the final treatment session. During each post-treatment session, participants will complete a 176-item naming assessment, one connected speech probe, and a strategy knowledge probe.

Phase 1) Pre-treatment:

a) Cognitive-linguistic assessments. Eligible and consented participants will complete a battery of standardized cognitive-linguistic assessment, including:

- The Western Aphasia Battery-Revised (WAB-R)⁴⁶,

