- General Health Questionnaire-12³⁵,
- Stroke and Aphasia Quality of Life Scale⁴¹,
- Subtests of the Cognitive Linguistic Quick Test-Plus (CLQT+)³⁹,
- The Metalanguage in Aphasia Assessment⁴⁰ (MetAphAs),
- The Communication Confidence Rating Scale for Aphasia (CCRSA),
- The Scenario Test⁸⁶

All assessments will be administered via paper and pencil, unless the participant is participating remotely. If they participate remotely, a fully encrypted device will be utilized but all responses will still be collected via paper and pencil.

b) Naming assessments and connected speech probes: Participants will complete three pretreatment naming assessments to establish a stable baseline⁸³ (*Figure 1*). During each baseline session, participants will complete a 176-item naming assessment and one connected speech probe. The 176-item naming assessment has objects from eight categories: animals, clothing, fruits and vegetables, occupations, household objects, other foods, tools. and transportation^{37,45,51}. Participants will be asked to name each object. To elicit connected speech, we will ask participants to verbally describe a picture, weekly activity, and/or personal memory (e.g., Tell me all about your weekend). Naming assessment and connected speech probe coding: We will calculate naming accuracy from the naming assessments and transcribe participants' prenaming verbalizations in order to later analyze and characterize their pre-treatment naming attempts. We will also transcribe and analyze participants' connected speech samples using Correct Information Unit (CIU) analysis⁶⁴, which provides measures of communicative efficiency and informativeness. Treatment and naming probe object selection: Participants' performance on the three pre-treatment naming assessments will determine which objects are either: trained during treatment, included in weekly naming probes, or untrained and used to test for deneralization post-treatment. Any objects a participant is unable to name on one, two, or three assessments will be included in the participant's object list. Of the included objects, we will create separate treatment and naming probe object lists taking into account the objects' semantic category and complexity.

Phase 2: Treatment

Each treatment session will have three sections:

- Strategy Education (~ 15 minutes),
- Naming Treatment Plus Strategy Application (~40 minutes),
- Strategy Debrief (~15 minutes).

Strategy Education. The clinician will:

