During treatment data: During treatment, we will collect treatment session data and weekly probe data. Weekly probe data will be the exact same as the pre- and post-treatment naming and spontaneous speech probe data (naming accuracy, circumlocution attempts, verbatim transcriptions), in addition to strategy knowledge data probes (i.e., asking participants to identify as many of the six strategy components as possible). These weekly probes will occur once per week for the eight weeks of treatment. During the Strategy Education section of treatment, data will include quantification of strategy component knowledge (out of a possible six). During the Naming Treatment Plus Strategy Application section of treatment, data will include: Percent of items participant correctly identified whether they would be able to name the object before attempting to name it, naming accuracy before feature generation, number of features generated by the participant per item, number of correctly matched features with feature types per item, number of additionally identified feature types per item, and naming accuracy after feature generation. During the Strategy Debrief section of treatment, data will include: transcription of participant's reaction and opinion of treatment session and number of home-based opportunities identified by the participant in which they could use the strategy.

VI. BIOSTATISTICAL ANALYSIS

a. Specific data variables being collected for the study.

Cognitive-linguistic assessments (pre-treatment and post-treatment): Language and cognitive assessments will be scored based on standardized norms and methods of administration and scoring provided in testing manuals. Cognitive-linguistic assessments and inperson treatment sessions will be videotaped to provide a measure of reliability of scoring and administration of assessments and treatment.

Naming, spontaneous speech, and strategy knowledge probes (pre-treatment, during treatment, and post-treatment): We will collect (1) naming accuracy, (2) verbatim pre-naming verbal naming attempts, (3) verbatim responses to spontaneous speech probes, and (4) number of identified strategy components.

Treatment data: We will collect data on: (1) number of identified strategy components and (2) number of feature words during moments of naming difficulty.

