b. Study endpoints. The participant's participation with the study will end when they request to withdraw from the study, or after the post-treatment assessments have been completed, whichever occurs first.

c. Statistical methods.

We will use visual inspection⁶⁸, mixed-effects modeling, and effect size calculations to analyze all results. For visual inspection, we will use the conservative dual-criterion method^{20,27,82}. We will use mixed-effects modeling to estimate the extent to which treatment-specific factors (fixed effects), pre-treatment cognitive-linguistic measures (random effects), and participant-specific factors (random effects) explain post-treatment naming and connected speech outcomes. We will calculate effect sizes by subtracting a participant's average pre-treatment score from their average post-treatment score and dividing by the pre-treatment standard deviation⁸.

Aim 1a. Measure PWAs' naming accuracy for trained and untrained objects. We will calculate effect sizes to measure the effect of treatment on participants' naming accuracy for trained objects, untrained semantically-related objects, and untrained semantically-unrelated objects between pre- and post-treatment. Hypotheses: Consistent with prior studies, we expect that naming treatment will yield medium to large effects for trained objects. Additionally, we hypothesize that strategy training will result in an increase in circumlocution-facilitated naming for untrained unrelated objects and yield medium effects for all untrained objects, regardless of semantic relatedness.

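### The weekly naming probe list is never given in its own format before teaching starts, so a dual-criterion reading of the weekly series cannot separate a change of test from a response to treatment

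*Combined protocol and SAP*

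**What the plan says.** **Baseline.** Section V.a, Phase 1(b): "Participants will complete three pretreatment naming assessments to establish a stable baseline", and "During each baseline session, participants will complete a 176-item naming assessment and one connected speech probe".

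**List-building.** The same section uses the results of those three tests to choose the objects: "Any objects a participant is unable to name on one, two, or three assessments will be included in the participant's object list". It continues: "Of the included objects, we will create separate treatment and naming probe object lists". The length of the probe list is not stated.

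**Weekly series.** Section V.a, item 2: "Starting on Week 2, the first treatment session of each week will begin with a 30-minute assessment, consisting of a naming probe". That block also has to hold two further probes, one of strategy knowledge and one of connected speech. Section V.e gives a different count, "These weekly probes will occur once per week for the eight weeks of treatment", and adds "Weekly probe data will be the exact same as the pre- and post-treatment naming and spontaneous speech probe data".

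**Analysis.** Section VI.c opens by naming visual inspection, mixed models and effect sizes for all results, and specifies: "For visual inspection, we will use the conservative dual-criterion method". It does not state the number of points required, an error rate, or how baseline points for the weekly series are scored. Under Aim 1a only pre/post effect sizes are named for naming accuracy. Visual inspection is named specifically only for strategy-component knowledge, under Aim 1b.

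**The concern.** The dual-criterion method draws a mean line and a trend line from the baseline phase and asks whether enough treatment-phase points lie above both. It assumes that the same measurement is taken in both phases.

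Here the probe list cannot exist until the third baseline test has been scored, and no further pre-treatment session is described. By the first Week 2 probe, the participant has had a full week of teaching (three sessions). For the weekly naming series, three things therefore change at the phase boundary together with the start of treatment: the item mix (only objects missed at least once), very probably the test length, and the place in the session (the opening of a therapy visit rather than part of an assessment session of about 2 hours).

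The design has no control group, so nothing else in the weekly series could expose such a step. A participant could be called a responder, or a real responder missed, because the test changed.

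**Working it through.** The plan states no error rate for this rule, so there is no figure to reproduce.

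**1. Could the weekly probe be the full 176-item test?** The block is 30 minutes (V.a, item 2): 30 × 60 / 176 = 10.2 seconds per object, with nothing left for the other two probes. At 15 seconds per object, 176 × 15 / 60 = 44 minutes. A shorter list is a strong inference, though not a stated fact.

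**2. Number of points.** Baseline: 3 (Phase 1(b)). Treatment: Weeks 2 to 8 give 7 if all eight weeks are completed (V.a); V.e gives 8. If each point had an independent even chance of lying above the lines, 7 of 7 has probability 0.5^7 = 0.0078, and at least 7 of 8 has (8 + 1) / 256 = 0.035.

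**3. Effect of a step caused only by the change of test.** Simulation with no treatment effect. Assumptions not in the documents: 30-item list, true naming probability 0.40, binomial scores, both lines raised by 0.25 baseline SD, and the required counts shown.

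| Step at phase change (percentage points) | Flagged, 7 of 7 | Flagged, 7 of 8 |
|---|---|---|
| -5 | 0.3% | 0.9% |
| 0 | 1.7% | 4.5% |
| +5 | 6.6% | 14.3% |
| +10 | 17% | 30% |

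The zero-step rate exceeds the binomial figure because the lines are estimated from only three points.

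**4. The baseline scoring choice also matters.** Suppose item naming probabilities p are uniform on 0 to 1, with neither a treatment nor a format effect.
- Whole-test baseline: mean accuracy 50%.
- Probe items, baseline scores extracted from the selecting tests: (1/2 - 1/4) / (1 - 1/4) = 33.3%.
- The same items tested afresh: (1/2 - 1/5) / (1 - 1/4) = 40.0%.

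So the series steps down by 10 points if the whole test is plotted, and up by 6.7 points if the extracted scores are plotted. Over six assumed distributions of item difficulty and a 40-item list, the extracted baseline steps up by 2 to 11 points, and the 7-of-7 rule flags 4 to 29% of series. This step comes from selecting failed items and would add to any format step.

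**5. Check of the fix.** With three baseline points taken after selection, on the same items and in the weekly format, the simulated flag rate is 1.6 to 1.9% (7 of 7) or 4.4 to 5.2% (7 of 8), close to the zero-step values.

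**The case against.** **The documents mention pre-treatment naming probes and identical data.** V.a, item 1, and V.e list naming probes before treatment, and V.e says "Weekly probe data will be the exact same as the pre- and post-treatment naming and spontaneous speech probe data". But Phase 1(b), the detailed description, gives only the 176-item test, and the bracket after the V.e sentence lists data types (accuracy, circumlocution attempts, transcriptions), not item sets. If the eighth probe counted in V.e were given at the start of Week 1, it would supply one own-format point before teaching. However, V.a starts the probes in Week 2, and one point cannot define a trend line or an SD. The wording needs reconciling; it does not close the gap.

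**An item-matched baseline exists.** This stands. The probe objects come from the 176, so each has three earlier scores. A reader might infer that the probe objects have no baseline at all; that is too strong. What is missing is a baseline in the weekly format, free of selection.

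**The rule may not be meant for naming.** This stands in part. Aim 1a names only pre/post effect sizes, and applying the dual-criterion rule to weekly naming rests on the general sentence in VI.c. Nor is that rule the only use of the weekly probes, since V.a also ties early stopping to them.

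**The format step is hypothetical.** This stands. Nothing in the documents shows that list length or place in the session changes accuracy.

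**Conclusion.** The gap is real: no administration of the finished probe list in its weekly format is described before teaching. A dual-criterion conclusion from the weekly naming series would therefore be confounded with the change of test. The concern applies only if the rule is used on that series, and its direction is open.

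The flag rates in the first simulation show sensitivity under assumed values. A reader might take 6.6% or 17% as this trial's false-positive rate, but the documents give no step size, probe length or required count from which to derive one.

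A reader might also infer that the main naming result is compromised by the format change. It is not: the Aim 1a pre/post effect sizes compare the 176-item test with itself.

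A third tempting inference is that the rule could simply be moved to the 176-item sessions by object set, with three pre-treatment points against five later ones and all five required (0.5^5 = 0.031). That does not work, because those three tests selected the objects on failure and so read low. With no treatment or format effect, simulation flags about 9 to 19% rather than the 3.2% found without selection. In the uniform case with 30 objects it flags 15.8%, against 11.1% for the weekly 7-of-7 rule. The count of five is also uncertain, since V.e speaks of six post-treatment sessions.

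**What to change.** 1. After list-building and before any teaching, give the finished probe list in its weekly format, for example on two occasions plus the start of Week 1. Use only those points as the dual-criterion baseline for the weekly naming series. Cost: up to three short probes per participant and a slightly later start.
2. If these probes are not added, show the weekly naming series descriptively and draw no dual-criterion conclusion from it. Cost: SAP wording only.
3. In either case, state the probe length, the number of points the rule requires, how baseline points are scored, and whether the rule applies to naming at all.
4. Reconcile three items of wording: the pre-treatment naming probes and identical-data statements (V.a, V.e) with Phase 1(b); the weekly probe count (seven implied by V.a, eight in V.e); and the post-treatment session count (six in V.e, against two retention sessions plus a repeat of the pre-treatment testing in V.a).

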Phase 4 post-treatment tests of retention: Participants will attend two additional post-treatment sessions one month and two months after treatment completion to evaluate retention. During these study visits, participants will complete naming assessment and a connected speech connected speech task in which we will ask participants to verbally describe a picture, weekly activity, or personal memory description (e.g., *Tell me all about your weekend*).

- b. Drugs to be used: N/A
- c. Devices to be used: N/A
- d. Procedures/surgical interventions: N/A

e. Data to be collected and when data is to be collected

Pre- and post-treatment data: All pre-treatment and post-treatment cognitive-linguistic assessment data will be collected during pre- and post-treatment assessment sessions. This data will be collected on each respective assessment material's proper test booklet. Data from pre- and post-treatment naming probes will include naming accuracy and circumlocution attempts (i.e., naming attempts). Data from pre- and post-treatment spontaneous speech probes will include verbatim transcriptions of each participant's responses to the spontaneous speech probes (e.g., *Tell me all about your weekend*). Naming and spontaneous speech probe data will be collected

during the three pre-treatment and six post-treatment sessions. Audio recordings of naming probes will be randomized and coded for accuracy.

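### Objects are listed because they were missed at baseline and are then scored against the same baselines, so selected lists show a naming gain with no treatment effect; the untrained set is not defined

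*Combined protocol and SAP*

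**What the plan says.** Section V.a, Phase 1(b) plans three baseline administrations of the 176-item naming assessment and makes them the basis for sorting objects: "performance on the three pre-treatment naming assessments will determine which objects are either" trained, probed weekly, or kept untrained to test generalization. The entry rule is "Any objects a participant is unable to name on one, two, or three assessments will be included" in the participant's object list, so only objects named on all three occasions are left out. Then: "Of the included objects, we will create separate treatment and naming probe object lists". No corresponding sentence says which objects form the untrained set.

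Section VI.c takes the "average pre-treatment score from their average post-treatment score and dividing by the pre-treatment standard deviation". Under Aim 1a this is applied to trained, untrained related and untrained unrelated objects, and the hypothesis is that treatment will "yield medium effects for all untrained objects, regardless of semantic relatedness". For visual inspection, "we will use the conservative dual-criterion method". Section V.e says that pre- and post-treatment naming data are collected "during the three pre-treatment and six post-treatment sessions". No pre-treatment naming session other than the three baselines is described. (Figure 1 is not available in the text.)

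**The concern.** The three baselines both select the objects and score them. Selecting on a miss removes every 3/3 result from the pre-treatment score, while nothing restricts the post-treatment score. This is regression to the mean built into the list. Section IV.c assigns everyone the same treatment, so no control group reveals the artefact, and Aim 1a rests on these within-person changes. The artefact grows with accuracy and with inconsistency of naming. It therefore differs between participants, and milder participants can look like better responders. For generalization, the main question of the study, even the sign of the change expected under no effect depends on a set that the plan leaves open.

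**Working it through.** The plan states no figure for this, so there is none to reproduce.

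**Inputs from the documents.** Three baselines of 176 objects and listing after at least one miss (V.a). Effect size d = (mean post − mean pre)/pre SD (VI.c). Eligibility of 1 to 146 correct on the first assessment, at most 146/176 = 83.0% (III.a). Weekly probes: "Starting on Week 2, the first treatment session of each week will begin with a 30-minute assessment, consisting of a naming probe", which gives 7 probes over Weeks 2 to 8.

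**Assumptions.** No treatment or practice effect; a 30-object list; three post-treatment sessions; p spread over objects as a Beta distribution; 6,000 simulated participants per case. Some cases add session-to-session variability with SD 0.5 on the logit scale.

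**One object.** P(listed) = 1 − p^3. Expected pre score given listing = (p − p^3)/(1 − p^3). Expected post score = p. The difference is p^3(1 − p)/(1 − p^3) = p^3/(1 + p + p^2). At p = 0.5: 0.125/1.75 = 7.1 percentage points (42.9% to 50.0%). At p = 0.2: 0.65 points. At p = 0.8: 21.0 points.

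**A list.** Null gain = (E[p^3] − E[p^4])/(1 − E[p^3]). For Beta(1,1): (0.25 − 0.20)/0.75 = 6.7 points. For Beta(4,1): (4/7 − 1/2)/(3/7) = 16.7 points.

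| Distribution of p | Mean accuracy | Null gain, points | Median d | Median d, session SD 0.5 | Share with d > 0.5 |
|---|---|---|---|---|---|
| Beta(0.5,4.5) | 10% | 0.5 | – | – | 35% |
| Beta(1,3) | 25% | 2.3 | 0.33 | 0.23 | 44% |
| Beta(0.1,0.3) | 25% | 1.8 | 0.44 | – | 48% |
| Beta(1,1) | 50% | 6.7 | 0.88 | 0.56 | 68% |
| Beta(2,2) | 50% | 7.1 | 0.89 | 0.54 | 68% |
| Beta(0.1,0.1) | 50% | 2.4 | 0.58 | – | 53% |
| Beta(0.02,0.02) | 50% | 0.6 | – | – | 43% |
| Beta(4,1) | 80% | 16.7 | 1.96 | 1.15 | 97% |
| Beta(0.4,0.1) | 80% | 7.2 | 1.09 | – | 76% |

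The last column is without session variability; an unselected list gives about 30%. It counts a positive change over a zero pre SD as above the cutoff. That matters mainly for Beta(0.02,0.02), where 23% of lists have zero SD: its shares above d = 2 and d = 4 fall from 12% and 10% to 2% and 0% when these lists are dropped. With session SD 0.5, the shares above 0.5 for Beta(1,3), (1,1), (2,2) and (4,1) are 39, 52, 52 and 84%.

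**Untrained set, three readings.**
- Listed objects not trained: the same upward bias.
- Every object not trained: all 176 objects together have zero expected change (ignoring the eligibility cap), so the other 176 − 30 = 146 change by −30 × gain/146. This runs from −30 × 0.51/146 = −0.1 to −30 × 16.67/146 = −3.4 points. In d the medians are about −0.06 to −1.4, and in the worst case 79% of null participants fall below −0.5.
- Only objects named 3/3: the pre score is 100% and its SD zero, so d is undefined. For Beta(1,1) the expected post score is 0.20/0.25 = 80%, a fall of 20 points.

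**Dual criterion on a selected probe list** (assumed: lines raised by 0.25 SD, 7 of 7 points above both). Null positives are 4, 11, 11 and 39% for Beta(1,3), (1,1), (2,2) and (4,1), against about 2% unselected. With session SD 0.5 they are 2, 6, 5 and 18%.

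**Check of the remedy.** Scoring each baseline only on objects missed in at least one of the other two gives a null gain of −0.05 to +0.30 points. With session SD 0.5 it is −0.05 to +0.13, except near the cap: +1.67 for Beta(4,1) and +0.69 for Beta(0.4,0.1). The remainder arises because the cap itself selects on baseline 1. Using baselines 2 and 3 only gives −0.20 to +0.08, and −0.09 to +0.07 with session variability.

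**The case against.** The strongest reply is about size. List length, the distribution of p, session variability and the cutoff for a medium effect are all assumed. In severe impairment the artefact is about half a point, and 35% rather than 30% of null participants pass d = 0.5. The large figures sit near the eligibility cap and shrink with session variability. At d > 4 the excess is small except there: 17% against about 3% for Beta(4,1) without session variability, 7% with it. All of this stands. It limits how material the bias is, not its direction.

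A second reply is that the remedy no longer equals the effect size in VI.c, because numerator and denominator use different object sets, and that it is weakest near the cap. Both are true. The first must be stated when results are reported; the second is why the version from baselines 2 and 3 is needed.

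A third reply is that the dual-criterion rates rest on assumed settings, and that VI.c names visual inspection by aim only for strategy knowledge, although its opening covers all results. That stands, so those rates are illustrative.

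A reader might infer that the untrained set surely shares the upward bias. The text does not settle this: the sentence drawing lists from the included objects names only treatment and probe lists. A reader might equally dismiss the alternative because the change is only a few points. On the plan's own scale, d, it is not small.

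**Conclusion.** The concern holds for Aim 1a. Any list drawn from the selected objects has a positive expected gain with no treatment effect, unless naming is perfectly consistent; the entry rule itself provides for objects named on some occasions and missed on others. Under the assumptions above the gain is about 0.5 to 17 points, with median d from about 0 to 2. If the untrained set is every object not trained, the generalization hypothesis is biased towards failure. Normalized change scores (VI.c, additional analyses) inherit the bias if computed on these lists.

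A reader might infer that gains reported under this plan would be mere artefact, or that null participants would usually reach a medium effect. The documents do not support that: they fix neither the size nor a cutoff. Nor are Aims 1b and 2 affected, since they use feature words in the naming assessments, strategy knowledge and connected speech rather than list accuracy. The point should be settled before post-treatment data are seen; how much it matters depends on the participants enrolled.

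**What to change.** In VI.c:

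1. Define the untrained related and unrelated sets as listed objects not allocated to treatment, so that trained and untrained sets follow one selection rule.
2. For both, score each baseline session only on set objects missed on at least one of the other two sessions. Subtract this from the mean post-treatment score on those same objects, average the three differences, and divide by the SD of the fixed list's three baseline scores. Note that numerator and denominator use different object sets.
3. Report the same score from baselines 2 and 3 only as a sensitivity analysis, and rely on it for participants near the 146-item cap, where step 2 leaves up to about 1.7 points.
4. Use the same pre-treatment score for any list-based normalized change, and state that list-based dual-criterion results carry the selection bias.
5. When the pre-treatment SD is zero, report d as undefined and give the change in points.
6. Report the unselected 176-object change as a supporting result, noting that it includes trained objects.

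In V.a, allocate listed objects by semantic category and complexity, not by baseline score; step 2 depends on this.

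**Cost.** No new data. The standard error of the list gain rises by about 0 to 36% with three post-treatment sessions and 2 to 49% with six; for baselines 2 and 3 only, by 9 to 48% and 14 to 63%. Matching lists on baseline accuracy is ruled out, and reported gains become smaller. Near the cap the untrained set may be small: a participant who names the same 146 objects every time has only 176 − 146 = 30 listed.
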